Aims/Objectives: *The primary aim of this study is to determine the sensitivity and specificity of the RRT performed in a pediatric ophthalmology clinic, according to standardized practice guidelines, for detecting both anterior and posterior segment pathology in the pediatric population. The secondary aim of this study is to evaluate the impact of pharmacologic dilation on the sensitivity and specificity of the RRT in detecting anterior and posterior segment pathology in the pediatric population. We hypothesize that the sensitivity and specificity of the RRT will be sufficient for detecting anterior segment pathology but will be insufficient for detecting posterior segment ophthalmologic pathology with or without pharmacologic dilation.*

Study Population: *The study population will include pediatric patients under 17 years old recruited in clinical practice with known anterior or posterior segment pathology as well as patients without anterior or posterior segment pathology. In order to determine sensitivity and*

specificity of anterior and posterior segment pathology separately, we will split the patients with pathology into two groups, anterior and posterior.

Ophthalmology residents who are blinded to the patient's ophthalmologic diagnosis (or lack thereof) will perform the standardized RRT, which includes both a lights on and lights off examination

- Study Site(s):** *Children's National Health System and Fairfax*
- Number of Participants:** *100-200*
- Accrual Ceiling:** *200. We estimate that all consented subjects will be able to participate in this routine vision exam.*
- Study Duration:** *This study is expected to be completed within one year.*
- Subject Duration:** *The subject duration is expected to be one outpatient clinic visit.*

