There is ample evidence in the literature validating the RRT as a useful screening tool for pediatric anterior segment ocular pathology, with consistently high sensitivity and specificity. However, studies describing its utility in detecting posterior segment disease are lacking. Two recent studies have attempted to address this issue. Sun and colleagues used the RRT to screen over 7000 newborns followed by retinal imaging using a Retcam-3 with pharmacologic pupillary dilation. They found that for anterior segment disease, the RRT had a sensitivity of 99.6% (95% CI 97.1%-100%) compared to only 4.1% (95% CI 3.3%-5.1%, $\chi^2 = 1521.382$, $\phi = 0.836$, $P < .001$) for posterior segment pathology. In a similar study, Ludwig and colleagues detected posterior segment pathology in 49 of 194 eyes examined using the Retcam-3 with pharmacologic dilation (sensitivity = 100%); however, no abnormalities were detected in this same set of eyes with the RRT performed by a pediatrician in the newborn nursery (sensitivity = 0%).

Based on these results, there is insufficient evidence that the RRT is an effective screening exam for detecting posterior segment pathology - even with physiologic dilation during the lights off portion of the RRT. It has been established that pupillary size and viewing angle certainly do impact the quality of a posterior segment exam. In a study by Li and colleagues, the rate of tumor detection in a model eye was optimized when viewing at an oblique angle through a maximally dilated pupil of 8 mm. Even under the darkest lighting conditions, physiologic mydriasis will be limited, and especially with introduction of the direct ophthalmoscope light for the RRT. The average infant scotopic pupil size is 3.8 mm \pm 0.9 mm in diameter. When light is shone from ophthalmoscope, pupils usually constrict by 2 mm. Pharmacologic dilation, however, is not currently included as part of the practice pattern guidelines outlining the RRT due to its perceived associated potential risks and side effects.

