3.2 Secondary Objective(s)

The secondary outcomes of this study will be the sensitivity and specificity of the RRT in detecting anterior segment or posterior segmented pathology following pharmacologic dilation.

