6.4 Description of Study Procedures/Evaluations

- *Medical history—ocular history from prenatal care and on will be obtained through the medical record or in person.*
- *Medication history—Current medications taken required.*
- *Physical examinations—Subject's red reflex and pupillary size will be examined using a direct ophthalmoscope in bright and dim room lighting conditions as well as before and after pharmacologic dilation. Automated vision screening using the Spot photoscreener will be performed before and after dilation.*
- *The results of the red reflex exam will be discussed with the patient during the clinic visit.*
- *Photographs of the subject's red reflex may be taken and edited to ensure anonymity. These photographs will allow for digital analysis of the patients red reflex. These photographs will be kept on password*

protected computers at Children's National Health System and on password protected encrypted flash drives. These photographs may be used for dissemination of study results such as in conference abstracts and medical journals. Once the study is complete, original photographs may be destroyed.

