8.4 Description of Statistical Methods

To assess our primary and secondary hypothesis, sensitivity and specificity of the red reflex test (RRT) will be determined along with their 95% confidence interval using contingency tables for both anterior and posterior segment pathology. Positive predictive value (PPV), negative predictive value (NPV), and area under ROC curve (AUC) will also be determined. We will also compare sensitivity and specificity of RRT for both anterior and posterior pathology between with and without pharmacologic dilation using two-sided McNemar's test for correlated proportions.

All statistical tests will be two-sided and will be performed at the 5% level of significance unless otherwise stated. Stata 15.1 software will be used for all statistical analyses.

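### Dilated and undilated RRT results are compared only by a McNemar test of unstated version, with no estimate or confidence interval for the paired gain

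*Combined protocol and SAP*

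**What the plan says.** The secondary aim in the Protocol Summary is to "evaluate the impact of pharmacologic dilation on the sensitivity and specificity of the RRT". Section 3.2 gives the secondary outcome as "sensitivity and specificity of the RRT in detecting anterior segment or posterior segmented pathology following pharmacologic dilation".

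Section 8.4 handles this in two parts:
- Estimation: "To assess our primary and secondary hypothesis, sensitivity and specificity of the red reflex test (RRT) will be determined along with their 95% confidence interval".
- Comparison: the plan will "compare sensitivity and specificity of RRT for both anterior and posterior pathology between with and without pharmacologic dilation using two-sided" McNemar's test. The level is set by "All statistical tests will be two-sided and will be performed at the 5% level of significance unless otherwise stated".

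No section gives a paired difference, an interval for it, a smallest gain of interest, an expected discordance rate, or a choice between exact and chi-square McNemar. The sample size in Section 8.5 concerns interval width for single proportions.

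Section 2.1 argues that pupil size affects the posterior examination, citing a model-eye study in which tumor detection was "optimized when viewing at an oblique angle through a maximally dilated pupil of 8 mm". Section 6.4 says that the "red reflex and pupillary size will be examined using a direct ophthalmoscope in bright and dim room lighting conditions", and also before and after dilation. No analysis section uses pupil size.

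**The concern.** The aim asks how much dilation changes the test. A McNemar p-value says only whether a change was detected. The two condition-specific intervals come from the same children and ignore the pairing, so neither they nor their overlap give the uncertainty of the gain.

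The framing raises the stakes. The Protocol Summary predicts that the RRT will be insufficient for posterior pathology whether or not the pupil is dilated. Section 8.2 puts significant improvement under dim light or dilation into the null hypothesis. A non-significant McNemar result would then appear to support the investigators' expectation, when it may only reflect few discordant pairs. Few such pairs are realistic if undilated posterior sensitivity is near the 0% and 4.1% cited in Section 2.1 and dilation adds only a modest number of detections.

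**Working it through.** **1. The plan's own sample size.** Take the smallest n whose exact (Clopper–Pearson) 95% interval has total width at most 0.20, and divide by the share of patients it applies to.
- Sensitivity 90%: n = 44; 44 / 0.75 = 58.7, so 59.
- Specificity 80%: n = 70; 70 / 0.25 = 280.

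Both figures in Section 8.5 reproduce. Neither bears on the paired comparison.

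**2. Number of posterior cases (assumption).** The documents do not state it.
- Section 5.1: 200 − 100 controls = 100 with pathology; an even split gives 50.
- Section 8.5: 280 × 0.75 = 210; an even split gives 105.
- 25 and 75 show uneven splits of 100.

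**3. Fewest discordant pairs for exact significance.** If all m discordant pairs favour dilation, two-sided p = 2 × 0.5^m. For m = 5, p = 0.0625; for m = 6, p = 0.031. Fewer than 6 pairs can never reach 5%. With 50 cases and 10% discordance, P(fewer than 6) = 62%.

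**4. Power for a net 10-point gain.** The documents give no dilation effect, so two patterns are assumed: A, 10% gained and 0% lost; B, 11% gained and 1% lost. Power = Σ over m of P(m discordant) × P(test rejects given m), where m is binomial(n, gain + loss) and the number of gains given m is binomial(m, gain / (gain + loss)). Pairs are taken as independent.

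| Posterior cases | Exact, A | Exact, B | Chi-square, A | Chi-square, B |
|---|---|---|---|---|
| 25 | 3% | 4% | 24% | 24% |
| 50 | 38% | 35% | 75% | 59% |
| 75 | 77% | 65% | 95% | 78% |
| 105 | 96% | 85% | 99.5% | 91% |

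(Chi-square is without continuity correction.)

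**5. What the missing interval would show (50 cases, illustrative counts).** With b gains and c losses, the difference is (b − c)/n. The score (Tango) limits are the values δ that solve (b − c − nδ) / √{n[2q + δ(1 − δ)]} = ±1.96, with q the loss probability estimated under δ.
- 2 detected undilated, 7 dilated, b = 5, c = 0: gain 10 points, CI 2 to 21. Chi-square = 5²/5 = 5.0, p = 0.025; exact p = 0.0625. The verdict turns on a choice the plan leaves open.
- 3 detected undilated, 8 dilated, b = 6, c = 1: gain 10 points, CI −0.5 to 22. Chi-square = 5²/7 = 3.57, p = 0.059; exact p = 0.125. Neither version is significant, yet gains of about 20 points remain compatible with the data.

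**The case against.** A reader might infer that dilation is assessed by a p-value alone, with no effect size. The text does not support that: Section 8.4 plans estimates with 95% CIs for the secondary hypothesis too, so the level after dilation will be visible. In the first example, 7/50 is 14% with an exact CI of 6% to 27%, which shows low sensitivity whatever McNemar says. It would likewise be wrong to say that the aim goes unanswered. The absolute level is addressed; the size of the gain is not.

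Low power is not a given either. It depends on an unstated case count and test version, and at 105 cases even the exact test has 85–96%. The 35–38% at 50 cases belongs to the exact test recommended below. McNemar itself suits paired binary data.

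A reader might also infer that poor dilation will mask a real effect. No figure in the documents supports this. The Protocol Summary standardises the drops, and Section 5.3 excludes histories that affect normal pupillary reaction. A regression on pupil diameter could be unstable with few detections, restricting to eyes that enlarged would select on a response to the drops, and Section 6.4 does not specify recording in millimetres.

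These objections narrow the point, but none supplies the uncertainty of the paired gain.

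**Conclusion.** The point stands in a limited form. The plan estimates each condition but not the paired change, and the only dilated-versus-undilated comparison is a test of unspecified version. At the 200-patient enrolment with an assumed 50 posterior cases, power for a net 10-point gain is 35–38% (exact) or 59–75% (chi-square). A null result could be read as no benefit while gains near 20 points remain open. At 280 patients and 105 cases the problem largely eases, but Sections 5.1 and 8.5 disagree on which size applies.

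These figures rest on the assumed case counts, the assumed gain and loss rates, and one independent pair per patient. Sections 3.3 and 3.4 count eyes, so two eyes per child would add pairs but also correlation. The documents do not show that a null result will be misread, or that inadequate dilation is common. This is a worthwhile change to a secondary analysis; it does not undermine the design.

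**What to change.** In Section 8.4:
- Make the main dilation result the paired difference (dilated minus undilated) in sensitivity and in specificity, for anterior and posterior pathology separately, each with a 95% score-type CI for paired proportions and the two discordant counts.
- State that any conclusion of no benefit will rest on that interval and not on a non-significant p-value.
- Name exact McNemar as a supporting test only, and say that the interval governs if the two disagree. The 5-versus-0 example shows that they can.
- Summarise pupil size before and after dilation descriptively, and label any analysis of detection by pupil size as exploratory.

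No procedure or drop changes. The cost is SAP wording and a little more analysis work. The exact test is also more conservative than the chi-square version, which is why it should not carry the conclusion alone.

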8.5 Sample Size

*Our sample size calculation is based on our primary hypothesis. Assuming a 75% prevalence of anterior or posterior segment pathology and a sensitivity of 90% in our sample, a total of **59** patients will be required to construct a two-sided 95% sensitivity confidence interval with a width of at most +/-10%. Under the same assumptions, the sample size needed for a two-sided 95% specificity confidence interval of +/-10% around 80% is **280**. We will take the larger one of these two, which is **280**. The power analysis was carried out using PASS 2019 software.*

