The baseline demographic data will be presented descriptively. Continuous data will be summarized as mean with standard deviation or median with interquartile range depending on the distribution of the data. Categorical data will be summarized using frequencies with percentage. Summary demographic statistics between patients with and without eye abnormalities will be compared using unpaired t-test (normal) and/or Mann-Whitney U test (skewed) for continuous data, and Chi-square test and/or Fisher's exact test (if any of the expected cell frequencies are <5) for categorical data. Normality assumption will be checked by using statistical test (e.g., Shapiro Wilk test) as well as graphical methods (e.g., histogram, q-q plot).

To assess our primary and secondary hypothesis, sensitivity and specificity of the red reflex test (RRT) will be determined along with their 95% confidence interval using contingency tables for both anterior and posterior segment pathology. Positive predictive value (PPV), negative predictive value (NPV), and area under ROC curve (AUC) will also be determined. We

will also compare sensitivity and specificity of RRT for both anterior and posterior pathology between with and without pharmacologic dilation using two-sided McNemar's test for correlated proportions.

All statistical tests will be two-sided and will be performed at the 5% level of significance unless otherwise stated. Stata 15.1 software will be used for all statistical analyses.

*Our sample size calculation is based on our primary hypothesis. Assuming a 75% prevalence of anterior or posterior segment pathology and a sensitivity of 90% in our sample, a total of **59** patients will be required to construct a two-sided 95% sensitivity confidence interval with a width of at most +/-10%. Under the same assumptions, the sample size needed for a two-sided 95% specificity confidence interval of +/-10% around 80% is **280**. We will take the larger one of these two, which is **280**. The power analysis was carried out using PASS 2019 software.*

Section 1: Key Roles

Principal Investigator
[name], Vice-Chair, Ophthalmology
Children's National Health System
[name]
[contact]
[contact]

Performance	Performance Site PI	Describe Activities Conducted at
--------------------	----------------------------	---

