5.1 Study Population, Recruitment and Retention

Pediatric patients will be recruited through clinical practice at the designated study sites. Participants with known anterior segment or posterior segment pathology will be eligible for inclusion. Patients who have a history of disease, treatments and/or surgical procedures affecting the ability for normal pupillary reaction are excluded. An equal number of age matched participants with a normal anterior and posterior segment exam will be recruited from routine outpatient clinic visits. Informed consent will be obtained and will include an option to be considered for medical photography. Participants may opt out of photography and still be included in the study. For Spanish speaking participants, a telephone interpreter will be used for study recruitment and informed consent. A Spanish informed consent (developed by a Spanish medical translator from our English written consent) will be provided. Current estimated number of subjects required for the study is 200 total including 100 controls. Patient charts will be accessed from date of birth to patient's current age using either Cerner or Epic depending on the study site location. Examiners will include ophthalmology residents with one completed year of ophthalmology training. They will be blinded to participants' ophthalmologic history.

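### The adopted sample size of 280 at 75% pathology contradicts the accrual ceiling of 200 and the one-to-one plan in Section 5.1; restate one design and its precision

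*Combined protocol and SAP*

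**What the plan says.** Section 8.5 sets out its inputs as "Assuming a 75% prevalence of anterior or posterior segment pathology and a sensitivity of 90% in our sample". It asks for two-sided 95% intervals of ±10% and obtains 59 patients for a sensitivity of 90% and 280 for a specificity of 80%. It concludes: "We will take the larger one of these two, which is 280". The statistical part of the Protocol Summary repeats this: "the sample size needed for a two-sided 95% specificity confidence interval of +/-10% around 80% is 280".

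The enrolment plan differs. The Protocol Summary gives "Number of Participants: *100-200", and its accrual ceiling reads "200. We estimate that all consented subjects will be able to participate in this routine vision exam". Section 5.1 says "Current estimated number of subjects required for the study is 200 total including 100 controls" and fixes the ratio: "An equal number of age matched participants with a normal anterior and posterior segment exam will be recruited from routine outpatient clinic visits".

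Section 8.5 treats pathology as one pooled group, while the Study Population paragraph of the Protocol Summary says "we will split the patients with pathology into two groups, anterior and posterior". The size of each group is not given. Section 8.5 speaks of patients; Sections 3.3 and 3.4 count eyes.

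**The concern.** Two inputs conflict between current sections, and no text reconciles them. The first is the total: 280 is adopted, but no more than 200 may be accrued. The second is the mix: 75% pathology in the calculation, 50% in the recruitment rule. Cases and matched controls are recruited by design, so the share with pathology is set by the sponsor and is not an unknown prevalence.

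The mix matters because specificity is estimated from the controls alone. Staff who keep to the ceiling but aim for the 75% share, or who stop at the lower end of the 100-200 range, would miss the only specificity precision target in the plan. Staff who follow Section 5.1 would meet it. As written, there is no agreed point at which enrolment is complete, and the published justification would describe a design that was not run.

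**Working it through.** **Inputs.** Section 8.5: pathology share 75%, sensitivity 90%, specificity 80%, two-sided 95%, ±10%. Protocol Summary: 100-200 participants, ceiling 200. Section 5.1: 200 in total, 100 controls, equal numbers.

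**Method.** Exact Clopper-Pearson limits with x = n·p: lower = Beta quantile at 0.025 with parameters (x, n − x + 1); upper = Beta quantile at 0.975 with parameters (x + 1, n − x). The half-width is (upper − lower)/2. Here ±10 means a half-width of at most 10 points, that is, half the total width.

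**The plan's own figures.**
- Sensitivity 90%: the smallest n is 44 cases; 44/0.75 = 58.7, so 59.
- Specificity 80%: the smallest n is 70 controls; 70/0.25 = 280.

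Both match. Of the other intervals tried, Wald gives 47 and 248, Wilson 50 and 240, and continuity-corrected Wilson 60 and 280; none reproduces both.

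**The conflict.** 280 × 0.75 = 210 cases, leaving 70 controls; Section 5.1 gives 100 and 100. The excess over the ceiling is 280 − 200 = 80.

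**Precision under each reading** (patient as unit, half-widths in points):

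| Design | Cases | Controls | Specificity 80% | Pooled sensitivity 90% |
|---|---|---|---|---|
| 280 at 75% | 210 | 70 | 9.9 | 4.3 |
| 200 at 1:1 | 100 | 100 | 8.3 | 6.4 |
| 200 at 75% | 150 | 50 | 11.8 | 5.1 |
| 100 at 1:1 | 50 | 50 | 11.8 | 9.2 |
| 100 at 75% | 75 | 25 | 16.9 | 7.4 |

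Specificity needs at least 70 controls. The largest workable pathology share is therefore (200 − 70)/200 = 65% with 200 patients, and (100 − 70)/100 = 30% with 100.

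**Section 8.5 redone at one to one.** Sensitivity: 44/0.5 = 88 in total. Specificity: 70/0.5 = 140 in total.

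**The case against.** The strongest reply is that the conflict is harmless. Section 5.1 is the only place that fixes a recruitment ratio, and following it gives 8.3 and 6.4 points, inside both targets. That stands as a reason why the repair is cheap. It does not remove the conflict, because the plan nowhere says that 200 at one to one is its sizing basis; it says 280. A dropout allowance does not explain the gap either: the Protocol Summary expects every consented child to take part, and an allowance would put the ceiling above the required number.

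The convention for ±10 can be questioned. With 70 controls the exact interval is 68.7% to 88.6%, so the lower limit lies 11.3 points below 80%. If each limit had to be within 10 points, 65 cases and 87 controls would be needed, and 280 at 75% would itself miss. Half the total width is the convention that reproduces 59 and 280, so it is used here. The 100 + 100 design passes on either convention.

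The unit is also open. Section 8.5 attaches patients to 59 and gives 280 no unit of its own. Patients is the natural reading, but 280 eyes, at two per child, would be 140 children, inside the ceiling; the 75%/50% conflict would remain. If both eyes of m controls counted (an assumption), the effective n would be 2m/(1 + ρ), where ρ is the correlation between a child's two eyes. From ρ = 0 to ρ = 1 the specificity half-width would run from 5.8 to 8.3 with 100 controls, and from 8.3 to 11.8 with 50. The miss with 50 controls is therefore certain only at patient level.

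A reader might infer that 200 is too few, or that the separate anterior and posterior estimates miss ±10. The documents support neither. The first fails on the table above. For the second, no target per segment and no split are stated. Assuming an even split of 100 cases, 50 per segment give 9.2 points at 90%, and 3.9 and 6.7 at the 99.6% and 4.1% cited in Section 2.1. Only a value such as 50%, which is not in the documents, gives 14.5. An uneven split would be wider for the smaller group (13.5 at 90% with 25 cases).

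**Conclusion.** The contradiction is real and must be fixed: the adopted size exceeds the plan's own ceiling by 80, and its 75% input is incompatible with equal numbers of cases and controls. The fault lies in the inputs, not in the calculation. Depending on which section is followed, the specificity half-width runs from 8.3 to 16.9 points against a target of 10. This rests on the patient as unit, a true specificity of 80%, and ±10 read as half the total exact width. It is not evidence that 200 is inadequate: at one to one, 140 would meet both pooled targets. The unit of analysis, the unstated split by segment and the ranking of outcomes are side issues that affect what precision can be quoted; they are not separate grounds for this conclusion.

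**What to change.** State 200 as 100 cases and 100 controls consistently in the Protocol Summary (participants, ceiling, statistical paragraph), Section 5.1 and Section 8.5. Replace 280, 75% and the 100-200 range. Replace 59 as well, since it rests on the 75%: at one to one the stated targets need 88 in total for sensitivity and 140 for specificity.

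Then give the precision delivered, defined as half the total exact 95% width with the patient as unit: about ±8.3 points at specificity 80% and ±6.4 at pooled sensitivity 90%. Label the latter as pooled, and add precision per segment beside it once an anterior/posterior split is stated. If the eye is to be the unit, as Sections 3.3 and 3.4 imply, recompute these figures with allowance for correlation between a child's two eyes before quoting them.

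In the same revision, reconcile the outcome sections. Section 3.1 makes both segments primary and Section 3.2 makes accuracy after dilation secondary, whereas Section 3.3 lists posterior findings as primary and Section 3.4 anterior findings as secondary.

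Cost: no extra patients and no new procedures, but a protocol amendment that needs IRB approval before use (Section 10.2). The downside is that precision per segment, once stated, may be wider than the pooled figure. Keeping 280 instead would mean 80 more children, a higher ceiling and abandoning equal numbers.

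### Section 8.5 sizes the study with one 90% sensitivity and a pooled 75% prevalence, which fits neither the posterior hypothesis, the separate primary outcomes nor the 1:1 recruitment of 200 patients

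*Combined protocol and SAP*

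**What the plan says.** Section 8.5, repeated in the Protocol Summary, opens with "Our sample size calculation is based on our primary hypothesis". It continues "Assuming a 75% prevalence of anterior or posterior segment pathology" and adds "a sensitivity of 90% in our sample". From these it derives 59 patients for a "two-sided 95% sensitivity confidence interval with a width of at most +/-10" per cent. For a "two-sided 95% specificity confidence interval of +/-10% around 80" per cent it derives 280 patients, and it adopts 280 as the larger of the two.

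Other parts of the document bear on these inputs:

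- **Hypothesis.** The Protocol Summary expects the test to suffice for anterior pathology but states that it "will be insufficient for detecting posterior segment ophthalmologic pathology with or without pharmacologic dilation". Section 8.2 likewise expects poor posterior performance. Section 2.2 goes further and denies adequate sensitivity for either segment.
- **Evidence.** Section 2.1 cites one newborn study with 99.6% sensitivity for anterior disease, "compared to only 4.1" per cent for posterior disease. A second newborn study found 0% for posterior disease.
- **Outcomes.** Section 3.1 lists sensitivity and specificity for anterior pathology, and separately for posterior pathology, as primary outcomes.
- **Recruitment.** Section 5.1 plans equal numbers of cases and age-matched controls: "Current estimated number of subjects required for the study is 200 total including 100 controls". The Summary sets an accrual ceiling of 200.

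**The concern.** A precision calculation is only as good as the proportion and the group size put into it. Here a single sensitivity stands for two outcomes that the protocol expects to lie at opposite ends of the scale. For the posterior outcome, 90% is the reverse of what the study sets out to show.

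The 75% prevalence is also not the case share that will be recruited. Section 5.1 fixes that share at 50%, and no segment-specific share is given. As a result, section 8.5 does not tell the reader how precisely posterior sensitivity will be estimated, although that is the question motivating the study. The adopted total of 280 also follows from a case share that the design does not have.

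**Working it through.** **Inputs.** From section 8.5: sensitivity 0.90, specificity 0.80, prevalence 0.75, two-sided 95% intervals of ±10 points (total width 0.20). From section 2.1: 0.996 anterior; 0.041 and 0 posterior. From section 5.1: 100 cases and 100 controls.

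**Method.** Exact (Clopper-Pearson) interval at the expected count x = np. The lower limit is the 2.5% quantile of Beta(x, n − x + 1), set to 0 if x = 0. The upper limit is the 97.5% quantile of Beta(x + 1, n − x). Take the smallest n with total width at most 0.20. Like section 8.5, this counts one result per patient.

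**Step 1: reproduce the plan.**
- Sensitivity 0.90: 44 cases (interval 77.2% to 97.0%, width 0.198). 44 / 0.75 = 58.7, so 59.
- Specificity 0.80: 70 controls (68.7% to 88.6%, width 0.199). 70 / 0.25 = 280.

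Both figures match exactly, so the arithmetic is right for its inputs.

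**Step 2: cases needed at other sensitivities, same method.**

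| Sensitivity | Cases needed |
|---|---|
| 0% | 17 |
| 4.1% | 26 |
| 10% | 44 |
| 50% | 104 |
| 90% | 44 |
| 99.6% | 18 |

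The 44 cases behind the 59 fall short only for a sensitivity between about 10% and 90%.

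**Step 3: redo the comparison at the 1:1 share.**
- Specificity 80%: 70 / 0.50 = 140 in total, not 280.
- Sensitivity 90%, all cases counted together: 44 / 0.50 = 88 in total.
- Sensitivity 90%, planned per segment: 44 + 44 = 88 cases. With equal controls that is 176 in total, within the ceiling of 200.

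**Step 4: precision from the planned 100 cases and 100 controls.** The documents give no anterior/posterior split, so the number of cases in a segment is an assumption, shown over a range. Entries are total interval widths in percentage points.

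| True sensitivity | 25 cases | 50 cases | 75 cases |
|---|---|---|---|
| 4.1% | 20.4 | 13.3 | 10.5 |
| 99.6% | 14.5 | 7.9 | 5.6 |
| 90% | 27.0 | 18.5 | 14.9 |
| 50% | 40.9 | 29.0 | 23.6 |

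For specificity at 80%, 100 controls give 70.8% to 87.3%, a width of 16.5 points.

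**The case against.** The strongest defence has three parts.

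First, 59 is not the operative figure. The plan adopts 280, and at 75% pathology that means 0.75 × 280 = 210 cases, enough for a 20-point interval at any sensitivity, since even 50% needs only 104.

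Second, the values cited for posterior disease need fewer patients than 90% does.

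Third, 90% is compatible with the anterior half of the Summary's hypothesis.

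The second part stands in full. A reader might infer that, because 90% contradicts 4.1% and 0%, the 59 must be too small. The documents do not support that: the cited values need 26, 17 and 18 cases, all below 44. One can make 59 look too small by averaging the two segments. With an assumed half-and-half case mix the pooled sensitivity is (99.6% + 4.1%) / 2 = 51.9%, which needs 104 cases. But the documents state no such mix, and pooled sensitivity is not a primary outcome. Writing 104 cases into section 8.5 would plan for a quantity the study does not set out to report as primary.

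The first part does not rescue the section. The 210 cases exist only if 280 patients are enrolled at 75% pathology, and section 5.1 and the accrual ceiling rule out both. The third part covers one segment only, and section 2.2 contradicts it even there.

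**Conclusion.** The concern holds as a fault in the planning basis, not in the arithmetic. The 90% is unsupported for the posterior outcome and contradicts the hypothesis on which the section says it rests. The pooled 75% matches neither the separate primary outcomes nor the 50% case share of section 5.1. At that share the specificity requirement halves, from 280 to 140, and 90% sensitivity needs 88 in total or 44 cases per segment.

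The planned 200 patients are therefore not shown to be inadequate. With an assumed 50 cases per segment, the ±10-point target is met at 4.1%, 90% and 99.6%. It is missed if a segment's sensitivity is mid-range (29 points at 50%). It can also be missed if one segment is thinly represented: with 25 cases, the width is 27 points at 90% and just over 20 at 4.1%.

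These results assume the plan's exact interval, one result per patient, and the stated splits. The text should be corrected because it misdescribes both the basis and the precision of the study; the fault does not by itself invalidate the design.

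**What to change.** In section 8.5 and the Protocol Summary:

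1. Set a planning sensitivity for each segment, taken from the hypothesis and section 2.1, and state the expected number of anterior and posterior cases.
2. Redo the comparison at the 1:1 share. Replace 280 by 70 controls (140 in total) for specificity of 80%. Replace 59 by the case count for each segment's chosen sensitivity: 44 per segment if 90% is kept, or 88 patients in total if all cases count together.
3. State the precision that the planned enrolment delivers, per segment and including a mid-range value. With 50 cases per segment the widths are about 13 points at 4.1%, 8 at 99.6%, 18 at 90% and up to 29 at 50%. With 100 controls the width is about 17 points at 80% specificity.

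The cost is a rewrite of one paragraph in two places, with no added enrolment. The stated precision becomes less favourable for a mid-range sensitivity.
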